### **8.1.5 Treatment Beyond Disease Progression**

The IMPs used in this trial are meant to induce an immune response against the subject's tumor and may not have an immediate effect on the tumor. In addition, the expected mechanism of action involves an infiltration of T-cells and inflammatory cells and local release of inflammatory cytokines. Therefore it is expected that initial radiographic progression may not be indicative of subsequent lack of response. Treatment may continue in spite of early radiographic progression, including appearance of new lesions, in the absence of symptomatic progression as long as the subject meets the other criteria in Sections 8.1.2 and 8.1.3 and has not had an AE that meets the criteria for treatment discontinuation in Section 8.1.4. Treatment past initial RECIST-defined radiographic progression may continue according to Investigator judgment, in consultation with the Medical Monitor, based on the subject's overall clinical status, overall tumor burden, and rate of progression, taking into account the subject's other treatment options and need for urgent intervention. (As of Amendment 3, decisions regarding subject treatment should be made according to site standard of care as determined by the Principal Investigator.) For example, a subject may continue treatment if a tumor assessment shows improvement or stable disease compared to the previous scan, even if there is progression compared to the baseline scan. Investigators may schedule an additional tumor assessment within 6 weeks after a scan showing progression, in order to reassess the subject's response.

Subjects may be treated after progression if they meet these criteria:

- Investigator-assessed potential clinical benefit;
- No disease-related clinical deterioration;
- Absence of progressive tumor at critical anatomical sites (e.g., cord compression) requiring urgent alternative medical intervention;
- Subject meets other re-dosing criteria in Section 8.1.3 and has not had an AE that meets the criteria for treatment discontinuation in Section 8.1.4.

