#### **Secondary Endpoints:**

- Best overall response (BOR) evaluated using RECIST v. 1.1. BOR is defined as the best response designation recorded between the date of first dose of IMP and the date of subsequent anti-cancer therapy (excluding on-treatment palliative radiotherapy of non-target bone or CNS lesions). Note: Continuation of nivolumab after discontinuing combination therapy does not count as start of new therapy for this definition. A BOR of CR or partial response (PR) requires confirmation of the assessment at least 4 weeks later.
- Time to response (TTR): Days from Cycle 1 Day 1 through the first assessment date of confirmed CR/PR using RECIST v. 1.1;
- Duration of response (DOR): Days from the first assessment date of confirmed CR/PR through the date of death or PD, whichever is earlier using RECIST v. 1.1;
- Progression-free survival (PFS): Days from Cycle 1 Day 1 through the date of death or PD, whichever is earlier. For subjects whose BOR is PR or CR using RECIST v. 1.1, the date of first documentation of objective tumor progression or death which occurs after the last documentation of PR or CR will be used as the event date for PFS;
- Overall survival (OS): Days from Cycle 1 Day 1 until the date of death.

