- Progression-free survival (PFS): Days from Cycle 1 Day 1 to the date of death or PD using RECIST v1.1, whichever is earlier. Clinical deterioration in the absence of objectively documented progression per RECIST 1.1 is not considered progression for the purpose of determining PFS. Subjects who die without a reported progression will be considered to have progressed on the date of their death. Subjects who did not progress or die will be censored on the date of their last evaluable tumor assessment. Subjects who did not have any on study tumor assessments and did not die will be censored on the date of first dose. Subjects who started any subsequent anti-cancer therapy, including tumor-directed radiotherapy and tumor-directed surgery, without a prior reported progression will be censored at the last evaluable tumor assessment prior to initiation of the subsequent anti-cancer therapy. For subjects whose BOR is PR or CR using RECIST v1.1, the date of first documented objective tumor progression or death that occurs after the last documented PR or CR will be used as the PFS event date.
- Overall survival (OS): Days from Cycle 1 Day 1 to the date of death. For subjects without documentation of death, OS will be censored on the last date the subject was known to be alive.

Exploratory Endpoints

- Pharmacokinetic parameters:
 - Mogamulizumab: observed minimum serum concentration at the end of a dosing interval (C_{\min}) and corresponding C_{\max} ; and
 - Nivolumab: C_{\min} .
- Immunogenicity: Anti-mogamulizumab antibody and anti-nivolumab antibody;
- Pharmacodynamic parameters: biomarkers may include, but are not limited to, immune cell subsets and factors such as cytokines and chemokines in tumor and/or blood;
- Immune-related overall response evaluated using irRECIST v1.1.

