PR	NE	SD provided minimum criteria for SD duration was met, otherwise, NE
NE	NE	NE

a: If a CR is truly met at first time point, then any disease seen at a subsequent time point, even disease meeting PR criteria relative to baseline, makes the disease PD at that point (since disease must have reappeared after CR). Best response would depend on whether minimum duration for SD was met. However, sometimes ‘CR’ may be claimed when subsequent scans suggest small lesions were likely still present and in fact the patient had PR, not CR at the first time point. Under these circumstances, the original CR should be changed to PR and the best response is PR.

CR=complete response; NE=not evaluable; PD=progressive disease; PR=partial response; SD=stable disease.

Time to Response (TTR)

Time to response will only be summarized descriptively for responders (i.e., CR or PR).

Duration of Response (DOR)

Duration of response will be calculated from the first date of confirmed CR/PR to the date of death or the date of first documented tumor progression (PD), whichever is earlier, using RECIST v1.1. Subjects who remain alive and do not progress will be censored on the date of their last tumor assessment. Subjects who start subsequent therapy without a prior PD will be censored at the last tumor assessment prior to initiation of the subsequent anticancer therapy. Response duration will only be evaluated in subjects with a BOR of CR or PR.

The median DOR, along with its two-sided 95% CI (Brookmeyer, 1982), will be estimated using the Kaplan-Meier (KM) method.

Progression-Free Survival (PFS)

PFS will be calculated as the number of days from the first dose of IMP to the date of death or PD, whichever is earlier. For subjects whose BOR is PR or CR using RECIST v1.1, the date of first documented objective tumor progression or death that occurs after the last documented PR or CR, and prior to the start of post-treatment anti-cancer therapy will be used as the PFS event date. Subjects who die without a reported prior progression will be considered to have progressed on the date of their death. Subjects who remain alive and do not progress will be censored on the last tumor assessment date. Subjects who start subsequent therapy without a prior reported progression will be censored on the date of last tumor assessment prior to initiation of subsequent anticancer therapy. Subjects who have no post-baseline tumor assessments and do not die will be censored on Day 1.

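### PFS passes over a progression that precedes a responder's last CR or PR and, unlike BOR, TTR and DOR, has no version based on first progression

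*SAP*

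**What the plan says.** **Event rule.** Protocol 10.1 states that for responders "the date of first documentation of objective tumor progression or death which occurs after the last documentation of PR or CR will be used" to date PFS. SAP 4 repeats this: the event "after the last documented PR or CR will be used as the PFS event date". SAP 4.9.1 has the same rule, dating PFS to "the date of first documented objective tumor progression or death that occurs after the last documented PR or CR", with one added limit: "and prior to the start of post-treatment anti-cancer therapy will be used as the PFS event date". All other subjects are dated to their first PD or death.

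**Why a PD can precede a response.** Protocol 8.1.5: "Treatment past initial RECIST-defined radiographic progression may continue according to Investigator judgment". The primary BOR in SAP 4 takes the best response up to subsequent anti-cancer therapy, whether or not PD has occurred.

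**First-PD versions.** SAP 4 and Table 14.2.1.2 define a BOR cut at first radiographic progression. Tables 14.2.2.1 and 14.2.3.1 have a second block for TTR and DOR cut at PD, and Listing 16.2.6.3.2 supports them. PFS has one block in Table 14.2.4.1, one Kaplan-Meier figure (14.2.1) and one progression date per subject in Listing 16.2.6.2.1. The DOR bullet in SAP 4 refers to a primary definition of PFS, but no second definition is given.

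**DOR and censoring.** In SAP 4.9.1, DOR runs "from the first date of confirmed CR/PR to the date of death or the date of first documented tumor progression (PD"), whichever is earlier. Two of its PFS censoring sentences matter here: "Subjects who remain alive and do not progress will be censored on the last tumor assessment date", and "Subjects who start subsequent therapy without a prior reported progression will be censored on the date of last tumor assessment" before that therapy.

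**The concern.** The same radiographic PD is a PFS event in a subject who never responds and is passed over in one who later responds. Which treatment applies depends on an outcome seen after the PD, and the change can only lengthen PFS. The SAP foresaw responses after PD and planned a first-PD version of every other response-related endpoint, so PFS is the one such endpoint for which no planned summary shows how much the choice matters.

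A smaller matter concerns the same subjects. The DOR wording does not say which PD ends the response. Nor does either censoring sentence, read literally, give a date to a responder whose only PD was skipped and who then has no qualifying event.

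**Working it through.** The plan gives no figure to reproduce here, so I applied the written rules to invented response sequences.

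**Inputs.** Scans at Week 10 and then every 12 weeks (Protocol Table 9-1). Day = 7 × week + 1, so Weeks 10, 22, 34, 46 and 58 are days 71, 155, 239, 323 and 407. Months = days / 30.4 (SAP 6.2.1), so the 3-, 6-, 9- and 12-month landmarks of Table 14.2.4.1 fall at days 91.2, 182.4, 273.6 and 364.8. DOR = PD date − response date + 1 (Listing 16.2.6.3.1). Cohort sizes are those of SAP Table 1: 32 + 21 + 21 + 29 + 36 + 28 + 17 = 184.

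**Sequences.**

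| Sequence | PFS by responder rule | PFS by first PD |
|---|---|---|
| A: PD 71, PR 155, PR 239, PD 323 | day 323 (10.6 months) | day 71 (2.3 months) |
| B: PR 71, PR 155, PD 239, PR 323, PD 407 | day 407 (13.4 months) | day 239 (7.9 months) |

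In A the skipped PD and the counted event lie on either side of the 3-, 6- and 9-month landmarks. In B they lie on either side of the 9- and 12-month landmarks.

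**Size per subject.** With no earlier censoring, the Kaplan-Meier estimate is the proportion still event-free. Moving one event from before a landmark to after it therefore adds 1/N.

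| N | 1 subject (1/N) | 2 subjects (2/N) |
|---|---|---|
| 36 | 2.8 points | 5.6 points |
| 21 | 4.8 points | 9.5 points |
| 17 | 5.9 points | 11.8 points |
| 184 | 0.5 points | 1.1 points |

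**When a landmark does not move.** Protocol 8.1.5 allows a rescan within 6 weeks of a PD, and confirmation needs only 4 weeks. Take PD on day 71, PR on day 71 + 42 = 113, confirmation on day 113 + 28 = 141, and PD on day 155. Both candidate event dates, 71 and 155, precede day 182.4, so the 6-month rate is unchanged. Only the 3-month rate rises.

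**DOR.** In B, DOR ends at the first PD after response: 239 − 71 + 1 = 169 days. Primary PFS for the same subject runs to day 407.

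**Censoring.** Take A up to day 239, then assume new therapy on day 260 and death on day 400.
- SAP 4: death is the first PD or death after the last PR, and the new-therapy censoring sentence does not apply because a PD was reported on day 71. Event at day 400.
- SAP 4.9.1: death falls after new therapy, so it is not an event. The subject did progress and did have a prior reported PD, so neither censoring sentence literally applies. The natural date, day 239, is not written.
- Difference: 400 − 239 = 161 days, and event against censored.

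**The case against.** The responder rule is the same in the protocol and both SAP sections apart from the therapy clause, and it fits a design that permits treatment past PD. PFS is secondary, single-arm and untested. Comparing CR/PR counts in Tables 14.2.1.1 and 14.2.1.2 shows how many subjects responded only after PD, and first-PD PFS can be rebuilt from the tumor assessment listing. SAP 1 allows added analyses in the CSR. All of this stands, and it is why the point is minor. It does not remove the gap: no planned PFS summary shows the difference, and the BOR comparison does not reveal subjects like B, who count as responders in both tables.

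Precision limits the practical effect. Assuming a true 6-month PFS of 20% to 40% (not a document figure) and no censoring, √(p(1−p)/N) is 8.7 to 10.7 points at N=21 and 6.7 to 8.2 at N=36. A single-subject shift of 4.8 or 2.8 points is well inside that. The shift nevertheless runs one way only.

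Three stronger readings are tempting but unsupported:
- *That the SAP departs from the protocol, or that the rule is a mistake.* Protocol 10.1 states it explicitly.
- *That DOR could come out negative.* Sequence A taken literally gives 71 − 155 + 1 = −83 days, but Appendix 1 section 5.1 measures duration from response to later recurrence or progression. This is a wording artefact, not a result the plan would produce.
- *That SAP 4 and SAP 4.9.1 disagree about every death after new therapy.* SAP 4 already censors subjects who start new therapy without a prior reported PD, so the two can be read consistently for ordinary responders. The difference is confined to responders with an earlier skipped PD.

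**Conclusion.** The point holds as a minor fix. Primary PFS can only equal or exceed time to first PD or death, the excess arises only in subjects who respond after a PD, and PFS alone among BOR, TTR, DOR and PFS lacks a first-PD version.

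The 1/N effect assumes no earlier censoring, a skipped PD before the landmark and a counted event after it. How many subjects meet those conditions is not in the documents; I expect few. The DOR and censoring wording leaves a programmer to choose dates for the same few subjects. The endpoint is descriptive, so only the reported PFS and DOR estimates are affected.

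**What to change.** **Main change.** Keep the protocol-defined PFS as primary. Add a sensitivity PFS: first RECIST v1.1 PD or death for every subject regardless of BOR, censored at the last evaluable tumor assessment before any subsequent anti-cancer therapy started without a prior PD. Show it as a second block in Table 14.2.4.1 and a column in Listing 16.2.6.2.1.

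**Wording, relevant only to responders with an earlier skipped PD.**
1. In SAP 4, SAP 4.9.1 and the note to Table 14.2.3.1, state that the PD ending DOR must follow the first response, as Appendix 1 section 5.1 already implies. Add that primary DOR and primary PFS may still end on different PDs; in sequence B they remain at days 239 and 407.
2. Use the same subsequent-therapy clause in SAP 4 and SAP 4.9.1. State that a responder with no qualifying PD or death after the last CR/PR and before new therapy is censored at the last evaluable assessment before that therapy. Identify this as a clarification of Protocol 10.1, which has no such clause, because it settles the day-400 death above as censored.

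**Cost.** One more Kaplan-Meier run, one table block, one listing column and a few SAP sentences; no new data. The reader has one more block to read, and the first-PD PFS may look slightly shorter.

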**Table 9-1 Schedule of Events: Screening and Treatment Periods**

Procedure b	Referenced Section(s) of Protocol	Screening	Cycle 1				Cycle 2		Cycle $\geq$ 3		EOT (Section 9.3)
			D1	D8	D15	D22	D1	D15	D1	D15	
Visit Window (days)		-28 to -1	-	$\pm 2$	$\pm 2$	$\pm 2$	-	$\pm 3$	-	$\pm 3$	
Pharmacokinetics	10.2		Refer to Table 10.2-1								
Anti-drug Antibody			Refer to Table 10.2-1								
Pharmacodynamics			Refer to Table 10.2-1								
Adverse Events	10.3	X	X	X	X	X	X	X	X	X	X
Prior/Concomitant Medications	8.5	X	X	X	X	X	X	X	X	X	X
Mogamulizumab Administration	8.1.1		X	X	X	X	X	X	X	X	
Nivolumab Administration	8.1.1		X		X		X	X	X	X	

a: Informed consent must be obtained prior to undergoing any study specific procedure that is not part of normal care. Data from procedures that were done as part of normal care may be used once the subject signs the ICF, provided they were done within the screening window.

b: Pre-dose (up to 30 minutes before SOI); and EOI ( $\pm 5$  minutes) of nivolumab; predose (up to 30 min before) SOI, every 15 ( $\pm 5$  minutes) during infusion; and EOI ( $\pm 5$  minutes) of mogamulizumab; hourly during the 4-hour post-infusion observation period.

c: Pre-dose (up to 30 minutes before SOI) of mogamulizumab, every 15 ( $\pm 5$  minutes) during infusion, and EOI ( $\pm 5$  minutes) of mogamulizumab, 30 minutes ( $\pm 5$  minutes) after EOI of mogamulizumab.

d: Pre-dose (up to 30 minutes before SOI); and EOI ( $\pm 5$  minutes) of nivolumab; predose (up to 30 min before) SOI, every 15 ( $\pm 5$  minutes) during infusion; and EOI ( $\pm 5$  minutes) of mogamulizumab; 30 minutes ( $\pm 5$  minutes) after EOI of mogamulizumab.

e: Day 1 labs can be done up to 3 days prior to dosing.

f: Tumor assessments by RECIST v. 1.1 will be performed at Screening, at Week 10, at least every 12 weeks thereafter until unequivocal disease progression or death.

g: Required at Screening (except as indicated in the inclusion criteria) and at Week 10 (unless the tumor is inaccessible for biopsy).

h: Procedures to be followed for subjects who are ongoing in the study (i.e., subjects who are continuing to receive study treatment or who are in safety or survival follow-up) at the time of data cutoff for completion of analyses are described in Section 9.5.

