## 4.2 Missing Assessments and Inevaluable Designation

When no imaging/measurement is done at all at a particular time point, the patient is not evaluable (NE) at that time point. If only a subset of lesion measurements are made at an assessment, usually the case is also considered NE at that time point, unless a convincing argument can be made that the contribution of the individual missing lesion(s) would not change the assigned time point response. This would be most likely to happen in the case of PD.

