4.9.1 Analysis of Efficacy Variables

Tumor response is determined by the investigator at each timepoint when tumor imaging is performed. All response-related endpoints (BOR, TTR, DOR, and PFS) will be based on RECIST v1.1 and derived programmatically using the investigator's assessments of tumor response at each timepoint. In addition, BOR of CR/PR will be assessed using irRECIST v1.1 criteria. The date of response is based on the image dates. In the event that there are images taken on different days, the latest date among all images taken will be used for the response date if the overall response is non-PD. If the overall response is PD, then the earliest date of all images taken will be used for the progression date.

All analyses will be conducted for the Efficacy Analysis Set.

Best Overall Response (BOR)

The number and percentage of subjects in each BOR category (i.e., CR, PR, SD, PD, and inevaluable) will be summarized. Subjects who do not meet CR/PR will be classified as stable disease if assessed as SD (or better) at least 9 weeks after first dose of IMP. The percentage of subjects with BORs of either CR or PR, taking into account any requirement for confirmation, will be calculated. The rates will be presented along with two-sided 95% exact confidence intervals. The 95% CIs will be derived using the Clopper-Pearson (Hollander, 1973) exact binomial confidence interval method.

The following Table 2 describes the derivation of BOR from overall response assessments at each visit. Note that BOR categories referenced in this table can be based on RECIST v1.1 or irRECIST v1.1 overall responses. For RECIST v1.1, BOR will be derived based on both

definitions as described in Section 4, secondary endpoints. For irRECIST v1.1 overall response, the analysis focuses on whether the subjects were responding (i.e., CR or PR) or not (i.e., not CR/PR).

Table 2 Best Overall Response When Confirmation of Complete Response and Partial Response is Required

Overall Response First Timepoint	Overall Response Subsequent Timepoint	Best Overall Response
CR	CR	CR
CR	PR	SD, PD or PR ^a
CR	SD	SD provided minimum criteria for SD duration was met, otherwise, PD
CR	PD	SD provided minimum criteria for SD duration was met, otherwise, PD
CR	NE	SD provided minimum criteria for SD duration was met, otherwise, NE
PR	CR	PR
PR	PR	PR
PR	SD	SD
PR	PD	SD provided minimum criteria for SD duration was met, otherwise, PD

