[2] Best overall response is defined as the best response designation recorded between the date of first dose of investigational medical product (IMP) and the date of subsequent anti-cancer therapy (excluding on-treatment palliative radiotherapy of non-target bone or CNS lesions).

[3] Sensitivity endpoint of Best overall response is defined as the best response designation recorded between the date of first dose of investigational medical product (IMP) to the first radiological disease progression or initiation of subsequent therapy, whichever occurred earlier.

Sum of existing and new target lesions.

- = Not available.

CR = Complete response; PR = Partial response; SD = Stable disease; PD = Progressive disease; UP = Unequivocal progressive disease.

Note: The date of overall response will be determined based on the image dates. In the event that there are images taken on different days, the latest date among all images taken will be used for the response date if the overall response is non-PD. If the overall response is PD, then the earliest date of all images taken will be used for the progression date.

Listing 16.2.6.2.1
 Progression-Free Survival (PFS) Per RECIST and Overall Survival (OS)

Treatment = Phase 1: Dose finding phase (Mogamulizumab 1 mg/kg + Nivolumab 240 mg)

Subject	Cancer Type	Date of First Dose	Progressive Disease?/ Date of Progression (Days [1])	Death?/ Date of Death (Days [1])	Date of Post Treatment Anti-Cancer Therapy	Date of Last Tumor Assessment (Days [1])	PFS (Days [1])	Date Last Known Alive (Days [1])	OS (Days [1])
xxx-xxx	Liver	YYYY-MM-DD	Yes/ YYYY-MM-DD (xx)	Yes/ YYYY-MM-DD (xx)	YYYY-MM-DD	YYYY-MM-DD (xx)	xxx	YYYY-MM-DD (xx)	xxx +
xxx-xxx	Renal Cell	YYYY-MM-DD	No	No	YYYY-MM-DD	YYYY-MM-DD	xxx +	YYYY-MM-DD (xx)	xxx
xxx-xxx	Sarcoma	YYYY-MM-DD	Yes/ YYYY-MM-DD (xx)	No	YYYY-MM-DD	YYYY-MM-DD	xxx	YYYY-MM-DD (xx)	xxx
xxx-xxx	Lung	YYYY-MM-DD	No	Yes/ YYYY-MM-DD (xx)	YYYY-MM-DD	YYYY-MM-DD	xxx	YYYY-MM-DD (xx)	xxx

Continue with Expansion phase (Mogamulizumab x mg/kg + Nivolumab 240 mg).

+ = censored observation; PFS = Progression Free Survival; OS = Overall Survival.

[1] Days = Date of specified event/assessment - Date of first dose + 1.

Note: Date of Last Tumor Assessment is the last tumor assessment prior to the start of post treatment anti-cancer therapy.

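### The SAP states the PFS and DOR censoring date twice, with and without 'evaluable'; followed literally, Section 4.9.1 lets a final not-evaluable scan extend progression-free time.

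*SAP*

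**What the plan says.** SAP Section 4, under the secondary endpoints, censors event-free subjects for PFS as follows: "Subjects who did not progress or die will be censored on the date of their last evaluable tumor assessment". A subject who starts new anti-cancer therapy without prior progression "will be censored at the last evaluable tumor assessment prior to initiation of the subsequent anti-cancer therapy". The same section censors DOR at the date used for the primary definition of PFS.

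SAP 4.9.1 restates these rules. For PFS: "Subjects who remain alive and do not progress will be censored on the last tumor assessment date". For new therapy, the subject "will be censored on the date of last tumor assessment prior to initiation of subsequent anticancer therapy". The DOR paragraph also uses the last tumor assessment, again without the word 'evaluable'.

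The notes to Listings 16.2.6.2.1 (PFS and OS) and 16.2.6.3.1 (TTR and DOR) read: "Date of Last Tumor Assessment is the last tumor assessment prior to the start of post treatment anti-cancer therapy". Protocol 10.1 defines PFS and DOR but gives no censoring rule.

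**The concern.** A scan can be performed and still leave disease status unknown. Protocol Appendix 1, Section 4.2, says: "If only a subset of lesion measurements are made at an assessment, usually the case is also considered NE at that time point". Such a scan carries a date, because SAP 4.9.1 provides that "the latest date among all images taken will be used for the response date if the overall response is non-PD", and NE is a non-PD result. SAP Table 2 lists NE as a timepoint response alongside CR, PR, SD and PD. SAP 4.9.1 also says the response endpoints are derived programmatically, so the wording decides which date the program selects.

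Two programmers working from the same SAP could therefore derive different PFS and DOR times for one subject. Under the wording of 4.9.1, a subject whose last scan is NE stays in the risk set as progression-free up to that scan, although the scan does not show it. Kaplan-Meier PFS rates at fixed times are planned by tumor type (Table 14.2.4.1) in cohorts of 17 to 36, so a few such subjects could be visible.

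**Working it through.** The plan states no PFS figure to reproduce. The check has three parts: when the rules differ, by how much for one subject, and what that could do to a Kaplan-Meier rate.

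**1. When the rules differ.** They differ only for a subject censored for PFS (event-free, or starting new therapy without PD) whose last relevant scan was done and rated NE. A visit with no imaging is also NE but has no image date, so it changes nothing. A later evaluable scan makes the two dates equal again.

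**2. One subject.** Protocol Table 9-1: "Tumor assessments by RECIST v. 1.1 will be performed at Screening, at Week 10, at least every 12 weeks thereafter". With first dose as Day 1, Week 10 is Day 71 and Week 22 is Day 155. Take SD on Day 71, NE on Day 155 and no further scan.

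- Section 4: censored at Day 71.
- 4.9.1 as written: censored at Day 155.
- Gap: 155 − 71 = 84 days; 84/30.4 = 2.76 months (the SAP converts at 30.4 days per month).

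If the only scan is an NE scan at Week 10, 4.9.1 censors at Day 71. Section 4 gives no date for this case. If it is read as censoring at first dose, the gap is 70 days, or 2.30 months.

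**3. Kaplan-Meier at 6 months (182.4 days), illustrations only.**

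*Small cohort.* N = 29 is the planned CRC size; the counts are assumed. Suppose 12 have PD at Week 10, 17 remain at risk and 8 have PD at Week 22, while k of the 17 have a final NE scan at Week 22.

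- 4.9.1: (17/29) × (1 − 8/17) = 31.0% for any k.
- Section 4: (17/29) × (1 − 8/(17 − k)) = 29.3%, 27.4%, 25.1%, 22.5% for k = 1, 2, 3, 4.

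*Large-sample version.* Assumptions: exponential time to progression with median 100 days; a fraction f of subjects have NE on the scan that would have shown PD and no scan afterwards; no deaths. Then:

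- p1, the proportion due to show PD at Day 71, is 1 − 0.5^0.71 = 0.3887, leaving 0.6113.
- p2, the proportion due to show PD at Day 155, is 0.6113 − 0.5^1.55 = 0.6113 − 0.3415 = 0.2698.
- 4.9.1: S = [1 − (1−f)p1] × [1 − (1−f)p2/0.6113].
- Section 4 (NE-only subjects at Day 1): S = [1 − (1−f)p1/(1 − f·p1)] × [1 − (1−f)p2/(0.6113 − f·p2)].

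| f | 4.9.1 | Section 4 | Difference |
|---|---|---|---|
| 5% | 36.6% | 35.6% | 1.0 |
| 10% | 39.2% | 37.2% | 2.0 |
| 20% | 44.6% | 40.6% | 4.0 |

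A simulation of the same set-up gave 36.9 vs 35.9, 39.1 vs 37.1 and 44.8 vs 40.8, in agreement to within 0.3 points. Under both rules and at all three values of f, the curve is above 50% after Day 71 (the lowest value is 62.3%) and below 50% after Day 155. The median is therefore Day 155 throughout.

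*Different assumptions.* With a 3-month median and each scan having a 5%, 10% or 20% chance of being NE and last, regardless of true status, simulation gave about 31% under Section 4 against 33.6%, 36.3% and 41.8% under 4.9.1.

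**The case against.** The strongest reply is that 4.9.1 is shorthand. Section 4 is where the endpoints are defined; it speaks of a primary definition of PFS, and 4.9.1 sends the reader back to Section 4 for the BOR definitions. That reading is natural and may be what was meant. But the back-reference is made for BOR, not for PFS or DOR censoring, and no text gives Section 4 precedence. The ambiguity stands.

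A reader might infer that the listings are built on the 4.9.1 rule. They do not show that. Their notes require only that the assessment precede post-treatment therapy, which fits either rule.

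A reader might also take 84 days as the amount for every affected subject. It is the planned maximum for one NE scan. Scans are at least every 12 weeks, Table 9-1 adds one at end of treatment, and follow-up scans continue until progression, new therapy, withdrawal of consent or death. A last scan can come well under 12 weeks after the one before it.

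The illustration is also built to show an effect: NE falls on the would-be PD scan and nobody returns. If half of those subjects had one evaluable scan 28 days later (also an assumption), the gaps fall to about 0.5, 1.0 and 1.9 points. In that model the Section 4 rule does not remove all the bias either: with no NE scans the 6-month rate is 34.2%, and Section 4 already gives 35.6% to 40.6%. These points limit the size, not the conflict.

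**Conclusion.** The conflict is real and minor. Section 4 and 4.9.1 give different PFS and DOR censoring dates for a subject whose last scan is NE, and the SAP does not say which applies. Read literally, 4.9.1 credits such a subject with up to one planned scan interval that no evaluable scan supports: at most 84 days (2.8 months) for a single NE scan, less with closer scans. Consecutive NE scans would add to it. The direction for landmark PFS is upward.

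The size cannot be fixed from the documents, which give no NE rate. The 1 to 4 points at 6 months for 5% to 20% NE is one illustration on the stated assumptions, with the median unchanged; other assumptions give smaller or larger gaps. The 70-day figure needs the added assumption that Section 4 censors an NE-only subject at first dose.

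The documents do not support claiming that reported PFS will be materially biased, or giving a size for DOR, which has the same conflict but was not computed. PFS and DOR are secondary and descriptive in single-arm cohorts. The Simon design uses response counts, so no test, futility rule or sample size changes.

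**What to change.** Use one rule in SAP Section 4, in SAP 4.9.1 (PFS and DOR, including the new-therapy sentences) and in the notes to Listings 16.2.6.2.1 and 16.2.6.3.1: *last evaluable tumor assessment (overall response other than NE); for PFS, if there is no evaluable post-baseline assessment, Day 1*.

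The last clause is needed because adding 'evaluable' alone would leave a subject with only NE scans without a date: the existing Day 1 rule covers only subjects with no post-baseline assessment. DOR needs no such default, since a confirmed responder has evaluable scans by definition.

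The cost is SAP wording and one filter in the derivation program. No new data are required.
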